# Section 9.4.1 Analyses to Evaluate Autoinjector

**Rationale for change:** To indicate that the results will be reported separately according to the format of the label being used.

#### Added text:

All analyses to evaluate the autoinjector will be reported separately for subjects using autoinjectors with labelling that includes a pictogram plus standard labelling elements or subjects using the standard labelling without the pictogram.

# 12.9.2. Protocol Amendment 01

Scope:

This amendment applies to all sites.

Protocol Changes specified in Amendment No.1 are summarised below.

Strike through text refers to deleted text and underlined refers to added text.

# **Protocol Changes**

# Section 1 Protocol Synopsis - Objective(s)/Endpoints

**Rationale for change:** To present the primary endpoint in a tabular format and include the secondary endpoint, as per GSK protocol template standard.

# **Revised text:**

The primary endpoint is the proportion of subjects successfully able to self-administer their observed third dose using the safety syringe at the clinic at Week 8.

The primary and secondary objectives and associated endpoints are outlined below:

Objectives	Endpoints
Primary	
• To assess the use of the combination product, mepolizumab liquid drug product in autoinjector for the subcutaneous self-administration of mepolizumab by subjects with severe eosinophilic asthma	• Proportion of subjects successfully able to self-administer their observed third dose at Week 8
Secondary	
• To assess the use of mepolizumab liquid drug product in autoinjector outside the clinic setting	• Proportion of subjects successfully able to self-administer their unobserved second dose outside the clinic setting at Week 4

# Section 4.1 Overall Design

**Rationale for change:** To refine the criteria for a successful injection following a userelated risk review

# **Revised text:**

- Autoinjector positioned with the yellow needle guard flat on the skin and pushed all the way down until a full dose is administered (for a full dose to be administered, the subject must either wait for the second click, the plunger to stop moving, the inspection window to be filled with the yellow indicator or hold the autoinjector down for a total of 15 seconds)
- Full dose administration: subject pushes the autoinjector all the way down and holds until either the second click, or the plunger stops moving and the inspection window is filled with the yellow indicator or pushes the autoinjector all the way down and holds for a total of 15 seconds

# Section 5.1 Inclusion Criterion No. 9/ Exclusion Criterion No. 15

**Rationale for change**: Included additional text to Inclusion Criterion 9 to allow Exclusion Criterion 15 to be removed:

# **Revised text:**

9. Gender: Male or Female

# Females:

A female subject is eligible to participate if she is not pregnant (as confirmed by a negative urine human chorionic gonadotrophin (hCG) test), planning to become pregnant during the time of study participation (and up to 16 weeks after the last dose), not lactating, and at least one of the following conditions applies:

**15. Pregnancy:** Subjects who are pregnant or breastfeeding. Patients should not be enrolled if they plan to become pregnant during the time of study participation (and up to 16 weeks after the last dose).

# Section 5.1 Exclusion Criterion No. 7

**Rationale for change:** To allow Bazett's to be used as the correction formula for heart rate when measuring the QT interval consistent with text elsewhere in the protocol.

# **Revised Text:**

7. ECG Assessment: QT interval corrected for heart rate by either Fridericia's or Bazett's formula  $QTc(F)/\underline{QTc(B)} \ge 450$ msec or  $QTc(F)/\underline{QTc(B)} \ge 480$  msec for subjects with Bundle Branch Block at Visit 1.

# Section 7.3 Assessment of Autoinjector Use

**Rational for change:** To refine the criteria for a successful injection following a userelated risk review

# **Revised text:**

At Visit 2 (Week 0), and at Visit 4 (Week 8), the investigator or designee will observe, using a checklist based on the autoinjector IFU, the ability of the subject/caregiver to (self)-administer the injection. The Observer Checklist (see SRM) will be used to determine if each step, according to the IFU, was completed easily, with some difficulty or not completed/intervention required.

Failure to perform one of the critical steps, i.e., correct choice of injection site, autoinjector positioned with the yellow needle guard flat on the skin and pushed all the way down until and a full dose is administered (for a full dose to be administered, determined by the subject must pushing the autoinjector all the way down and holding until either wait for the second click, or the plunger to stops moving, and the inspection window to be is filled with the yellow indicator or hold by the autoinjector being pushed all the way down and held for a total of 15 seconds) will be deemed to be a failure to successfully administer the injection.

# Section 10.7 Provision of Study Results to Investigators

**Rationale for change:** Delete text related to randomization codes as study is open-label and randomization codes will not be used.

# **Revised text:**

GSK will provide the investigator with the randomization codes for their site only after completion of the full statistical analysis.

# Section 11 References

Rationale for change: References not cited in the document.

## 1. INTRODUCTION

The purpose of this RAP is to describe the analyses to be included in the Clinical Study Report (CSR) for Protocol [204959](#):

Protocol Revision Chronology:		
2016N275054_01	18-AUG-2016	Original
2016N275054_03	13-OCT-2016	Amendment No. 1: Updated to refine the criteria for a successful injection, and amend exclusion criteria 7 and 15.
2016N275054_04	15-FEB-2017	Amendment No. 2: Updated to include a change to the labelling of the autoinjector in some geographical regions, and amend inclusion criteria 5.

All subjects in this study were recruited after the effective date of Protocol Amendment 2.

## 2. SUMMARY OF KEY PROTOCOL INFORMATION

### 2.1. Changes to the Protocol Defined Statistical Analysis Plan

An additional analysis population was defined for reporting screen failures and inclusion/exclusion criteria deviations. This population is described in Section [4](#).

There are no other changes to the protocol defined statistical analysis plan.

### 2.2. Study Objective(s) and Endpoint(s)

Objectives	Endpoints
Primary Objectives	Primary Endpoint

 
To assess the use of the combination product, mepolizumab liquid drug product in autoinjector, for the subcutaneous self-administration of mepolizumab by subjects with severe eosinophilic asthma.
 
	
 
Proportion of subjects successfully able to self-administer their observed third dose at Week 8.
 

Secondary Objectives	Secondary Endpoints

 
To assess the use of mepolizumab liquid drug product in autoinjector outside the clinic setting.
 
	
 
Proportion of subjects successfully able to self-administer their unobserved second dose outside the clinic setting at Week 4
 

Other Objectives	Other Endpoints

 
To assess the use of mepolizumab liquid drug product in autoinjector both inside and outside of the clinic setting.
 
	
 
Proportion of subjects successfully able to self-administer their observed first dose at Week 0
 
Proportion of subjects successfully able to self-administer both their unobserved second dose
 

Objectives	Endpoints
	and observed third observed dose at Weeks 4 and 8 
 
• Proportion of subjects successfully able to self-administer all three doses at Weeks 0, 4 and 8
 

 
• To evaluate autoinjector use & functionality.
 
	
 
• Device usability/functionality questionnaire completed at the End of Study/Early Withdrawal Visit
 

 
• To evaluate any autoinjector injection errors/failures related to use or device performance.
 
	
 
• Investigator evaluation of user/device errors
 
• Root cause analysis of each unsuccessful injection
 

 
• To characterise the subject experience of using the mepolizumab liquid drug product in autoinjector.
 
	
 
• Subject Exit Interviews completed over the telephone after the End of Study/Early Withdrawal Visit
 


 
• To assess mepolizumab plasma trough concentrations (<math>C_{trough}</math>) following the SC administration of mepolizumab liquid drug product in autoinjector.
 
	
 
• Mepolizumab plasma trough concentrations (<math>C_{trough}</math>) at Weeks 4, 8 and 12
 

 
• To assess the pharmacodynamic (PD) effect following the SC administration of mepolizumab liquid drug product in autoinjector.
 
	
 
• Ratio to baseline of blood eosinophils at Weeks 4, 8 and 12
 

 
• To assess the frequency of asthma exacerbations.
 
	
 
• Incidence of asthma exacerbations, expressed as the number of subjects with at least one exacerbation
 

Safety Objectives	Safety Endpoints

 
• To evaluate the safety and tolerability of mepolizumab liquid drug product in autoinjector.
 
	
 
• Incidence and frequency of Adverse Events (AEs) / Serious Adverse Events (SAEs) including systemic reactions and local injection site reactions
 
• Clinically significant change in haematological and/or clinical chemistry parameters
 
• Vital signs
 
• 12-lead electrocardiogram (ECG)
 
• Incidence of immunogenicity
 
• Level of self-reported pain immediately following, 1- and 24-hours following each injection (patient diary)
 

### 2.3. Study Design

Overview of Study Design and Key Features	

The diagram illustrates the study timeline. It begins with Pre-screening (0 to 2 weeks) and Screening (1 to 4 weeks). Key visits are marked: Visit 0 (Pre-screen), Visit 1 (Screen), and Visit 2 (Start of Study). Mepolizumab administration is shown as a series of doses: the first dose is administered in-clinic at Visit 2 (Week 0), the second dose is self-administered out-of-clinic at Visit 3 (Week 4), and the third dose is administered in-clinic at Visit 4 (Week 8). The study concludes at the End of Study (Week 12). A legend indicates that blue triangles represent 'In Clinic' and yellow triangles represent 'Out of Clinic'.
	

Design Features
	
 
• 12-week treatment period, open-label, single arm, repeat-dose, multi-centre study in subjects with severe eosinophilic asthma.
 
• Subjects (or their caregiver, if applicable) will be trained to administer mepolizumab liquid drug product in autoinjector prior to the first dose (Visit 2).
 
• Each autoinjector will have labelling that includes a pictogram plus standard labelling elements, or a standard labelling without the pictogram dependant on the country in which it is being used.
 
• Mepolizumab will be self-administered (by subject or caregiver, if appropriate) under observation in the clinic for first dose (Visit 2) and third dose (Visit 4). The second dose of mepolizumab will be self-administered (by subject or caregiver, if appropriate) at home without observation following Visit 3.
 
• All injections will be assessed by the investigator for success based on             
 
○ Direct observation of the self-administration if the dose was administered in the clinic, and inspection of the autoinjector.
 
○ Subject/caregiver completed checklist if the dose was administered outside the clinic, and inspection of the returned autoinjector.
 
 
 

Main Subject Entry Criteria
	
 
• Subjects aged 12 or older with physician diagnosis of asthma for <math>\geq 2</math> years.
 
 
Either
 
 
• Subjects receiving 100mg subcutaneous (SC) mepolizumab for the treatment of severe eosinophilic asthma every 4 weeks for at least 12 weeks prior to the study.
 

Overview of Study Design and Key Features	
	
or
 
 
Subjects not receiving mepolizumab treatment at Visit 1 meeting additional criteria of asthma of eosinophilic phenotype requiring regular treatment with high dose inhaled corticosteroids (ICS) in the 12 months prior to Visit 1, current treatment with an additional controller medication besides ICS for at least 3 months, and with one or more exacerbations in the 12 months prior to Visit 1.
 
 
Subjects are permitted to be enrolled without continuous high dose ICS, following discussion with the GSK Medical Monitor, providing the subject was receiving continuous ICS and the Investigator attests that the subject should have been treated with high dose ICS but this was precluded by financial or tolerance issues.

Dosing	
 
100 mg mepolizumab SC every 4 weeks (3 administrations) in thigh, abdomen or upper arm (caregiver only).
 

Treatment Assignment	
 
All subjects will receive the same treatment.
 
Autoinjector labelling will differ dependent on the country: subjects in the US, UK and Australia will use an autoinjector with a pictogram plus standard labelling elements, subjects in all other countries will use an autoinjector with standard labelling elements only.
 

Interim Analysis	
 
No interim analysis is planned.
 

Time and events	
 
See Appendix 1: Time & Events.
 

## 2.4. Statistical Hypotheses

The study is designed to descriptively evaluate the successful use of the mepolizumab liquid drug product in autoinjector for self-administration by subjects with severe eosinophilic asthma.

No formal statistical hypothesis testing is planned. Separate summaries of successful use will be provided for the group of subjects using labelling that includes a pictogram plus standard labelling elements, and the group of subjects using the standard labelling without the pictogram. The number and percentage of subjects successfully able to self-administer each mepolizumab dose will be reported, including 95% confidence intervals (CI). No comparison between the labels will be performed.

### **3. PLANNED ANALYSIS**

#### **3.1. Interim Analyses**

No interim analysis is planned.

#### **3.2. Final Analyses**

The final planned analyses will be performed after the completion of the following steps:

1. All subjects have completed the study as defined in the protocol.
2. All required database cleaning activities have been completed and final database release and database freeze (DBF) has been declared by Data Management.

## 4. ANALYSIS POPULATIONS

Population	Definition / Criteria	Analyses Evaluated
All Subjects Enrolled (ASE)	
 
All subjects for whom a record exists in the data base.
 
	
 
Pre-screen and screen failures
 

All Subjects (Safety)	
 
All enrolled subjects attempting at least one self-administration of mepolizumab.
 
	
 
Endpoints relating to autoinjector use and functionality, including primary endpoint
 
Study Population
 
Safety
 

Pharmacokinetic (PK)	
 
All enrolled subjects attempting at least one self-administration of mepolizumab for whom a PK sample was obtained and analysed.
 
	
 
PK
 

Pharmacodynamic (PD)	
 
All enrolled subjects attempting at least one self-administration of mepolizumab who had a baseline PD measurement and at least one post-treatment PD measurement.
 
	
 
PD
 

### NOTES :

- Please refer to [Appendix 8](#): List of Data Displays which details the population to be used for each display being generated.

### 4.1. Protocol Deviations

- Protocol deviations will be tracked by the study team throughout the conduct of the study in accordance with the Protocol Deviation Management Plan (PDMP).
  - Data will be reviewed prior to DBF to ensure all important deviations are captured and categorised on the protocol deviations dataset.
  - This dataset will be the basis for the summaries and listings of protocol deviations.
- Important protocol deviations (including deviations related to study inclusion/exclusion criteria, conduct of the trial, subject management or subject assessment) will be summarised and listed.
- A separate summary and listing of all inclusion/exclusion criteria deviations will also be provided. This summary will be based on data as recorded on the inclusion/exclusion page of the electronic case report form (eCRF).

## **5. CONSIDERATIONS FOR DATA ANALYSES AND DATA HANDLING CONVENTIONS**

### **5.1. Methods for Handling Centres**

In this multi-centre global study, enrolment will be presented by investigative site within country.

Each autoinjector will have labelling that includes a pictogram plus standard labelling elements, or a standard labelling without the pictogram. Centres in the US, UK and Australia will use labelling that includes a pictogram plus standard labelling elements, while centres in Canada, Germany, Netherlands, Russia and Sweden will use standard labelling without the pictogram. Separate summaries of successful use will be provided for the group of subjects using labelling that includes a pictogram plus standard labelling elements, and the group of subjects using the standard labelling without the pictogram.

### **5.2. Multiple Comparisons and Multiplicity**

No formal hypothesis will be tested in the study. Each endpoint will be considered separately and no adjustment for multiplicity will be made.

### **5.3. Handling of Missing Data**

In general, analysis will be performed on all available data and no imputation will be performed for missing data. However, if there are withdrawals from study treatment due to issues pertaining to the use of the autoinjector, sensitivity analysis of the primary endpoint will be performed. Missing injection success assessments for subjects withdrawing from study treatment due to issues with the autoinjector will be included in the analysis as injection failures i.e. as unsuccessful attempts to self-administer mepolizumab. Injection success assessments classed as “not attempted” on the eCRF for subjects withdrawing from study treatment due to issues with the autoinjector will also be included in this analysis as injection failures.

## 5.4. Data Display Standards

### 5.4.1. Study Treatment Descriptors

RandAll NG	Data Displays for Reporting	
Description	Description	Order
Not applicable	Liquid Autoinjector	1

### 5.4.2. Autoinjector Label Descriptors

Analyses to evaluate the autoinjector will be reported separately for the group of subjects using autoinjectors with labelling that includes a pictogram plus standard labelling elements, and the group of subjects using the standard labelling without the pictogram. Listings of autoinjector evaluation data will include the following label descriptions:

Reporting Group Descriptions – Autoinjector Label				
RandAll NG		Country	Data Displays for Reporting	
Code	Description		Description	Order
Not applicable		Australia, UK, US	Standard Label + Pictogram	1
		Canada, Germany, Netherlands, Russia, Sweden	Standard Label	2

### 5.4.3. Sub-group Display Descriptors

Data Displays for Reporting		
Subgroup Descriptor	Category	Order
Baseline Mepolizumab Use	No	1
	Yes	2
Injection Site	Abdomen	1
	Upper Arm	2
	Thigh	3

## 5.5. Other Considerations for Data Analysis and Data Handling Conventions

Table 1 provides an overview of the appendices within the RAP for outlining other general considerations for data analyses and data handling conventions.

**Table 1 Overview of Appendices**

Section	Component
Section 14.1	Appendix 1 : Schedule of Activities Protocol Defined Time & Events
Section 14.2	Appendix 2 : Study Phases and Treatment Emergent Adverse Events 
 
• Treatment Phases for Adverse Events
 
• Treatment Phases for Exacerbations
 

Section 14.3	Appendix 3 : Data Display Standards & Handling Conventions 
 
• Baseline Definition & Derivations
 
• Reporting Process & Standards
 

Section 14.4	Appendix 4 : Derived and Transformed Data 
 
• General
 
• Study Population
 
• Evaluation of Autoinjector
 
• Safety
 

Section 14.5	Appendix 5 : Reporting Standards for Missing Data 
 
• Premature Withdrawals
 
• Handling of Missing Data
 
• Handling of Missing and Partial Dates
 

Section 14.6	Appendix 6 : Values of Potential Clinical Importance

## 6. STUDY POPULATION ANALYSES

The study population analyses will be based on the “All Subjects (Safety)” population, unless otherwise specified.

Study population analyses including analyses of subject’s disposition, protocol deviations, demographic and baseline characteristics, concomitant medications and exposure will be based on GSK Core Data Standards. Details of the planned displays are presented in [Appendix 8: List of Data Displays](#).

## 7. ANALYSES TO EVALUATE AUTOINJECTOR

- All analyses will be based on the “All Subjects (Safety)” population.
- All analyses to evaluate the autoinjector will be reported separately for the group of subjects using autoinjectors with labelling that includes a pictogram plus standard labelling elements, and the group of subjects using the standard labelling without the pictogram. No comparison between the labels will be performed.

### 7.1. Primary Analysis

The primary endpoint is the proportion of subjects successfully able to self-administer their observed third dose at Week 8.

- The number and percentage of subjects successfully able to self-administer their observed third dose at Week 8 will be summarized together with 95% CI.
- The denominator for the percentage calculation will be the number of subjects attempting an injection at Week 8.
- CI for the percentages will be generated using the Exact (Clopper-Pearson) method for binomial proportions.
- No formal statistical analysis will be conducted and no comparison between labels will be performed.
- If a subject has more than one attempt to self-administer study treatment at Week 8, the first attempt will be included in the primary analysis. The best attempt will also be summarised as a supportive analysis. A separate listing of injection success for subjects who had more than one attempt to self-administer mepolizumab will be provided.
- If there are withdrawals from study treatment due to issues pertaining to the use of the autoinjector, a sensitivity analysis of the primary endpoint will be performed. Missing injection success assessments for subjects withdrawing from study treatment due to issues with the autoinjector will be included in the analysis as injection failures i.e. as unsuccessful attempts to self-administer mepolizumab. Injection success assessments classed as “not attempted” on the eCRF for subjects withdrawing from study treatment due to issues with the autoinjector will also be included in this analysis as injection failures.

Full details of data displays being presented in [Appendix 8: List of Data Displays](#).

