## 14.5. Appendix 5: Reporting Standards for Missing Data

### 14.5.1. Premature Withdrawals

Element	Reporting Detail
General	
 
• Subject study completion is defined as completion of the End of Study (Week 12) visit.
 
• Withdrawn subjects will not be replaced in the study.
 
• All available data from subjects who were withdrawn from the study will be listed and all available planned data will be included in summary tables and figures, unless otherwise specified.
 

Pre-Screen and Screen Failures	
 
• A subject will be assigned a subject number at the time when the informed consent form (ICF) is signed.
 
• A subject who is assigned a subject number but does not have any screening procedures at Visit 1 will be considered a pre-screen failure.
 
• A subject who completes at least one Visit 1 procedure but does not attempt to self-administer a dose of mepolizumab will be considered a screen failure.
 

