### 14.5.2. Handling of Missing Data

Element	Reporting Detail
General	
 
• In general, analysis will be performed on all available data and no imputation will be performed for missing data. However, if there are withdrawals from the study due to issues pertaining to the use of the autoinjector, a sensitivity analysis of the primary analysis will be performed. Missing or “not attempted” injection success assessments following these withdrawals will be imputed as injection failures i.e. unsuccessful attempts to self-administer mepolizumab in this sensitivity analysis.
 
• Missing data occurs when any requested data is not provided, leading to blank fields on the collection instrument. These data will be indicated by the use of a “blank” in subject listing displays, unless all data for a specific visit are missing in which case the data is excluded from the listing.
 
• Data below the limit of quantification (BLQ) is not missing data and must be displayed as such and included in all listings and summaries.
 

Outliers	
 
• Any subjects excluded from the summaries and/or statistical analyses because their values are considered outliers will be documented along with the reason for exclusion in the CSR.
 

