**14.8.2. Evaluation of Autoinjector**

No.	Population	IDSL / TST ID / Example Shell	Title	Programming Notes	Deliverable [Priority]
Evaluation of Autoinjector - Tables					
7.1	All Subjects	TAB_INJ1	Summary of the Proportion of Subjects Successfully Able to Self-Administer Injection by Visit – First Attempt Autoinjector with Standard Label + Pictogram	Add footnote: "Note: If a subject has more than one attempt to self-administer study treatment at a single visit, only the first attempt is included in this summary."	SAC
7.2	All Subjects	TAB_INJ1	Summary of the Proportion of Subjects Successfully Able to Self-Administer Injection by Visit – First Attempt Autoinjector with Standard Label	Add footnote: "Note: If a subject has more than one attempt to self-administer study treatment at a single visit, only the first attempt is included in this summary."	SAC
7.3	All Subjects	TAB_INJ1	Summary of the Proportion of Subjects Successfully Able to Self-Administer Injection by Visit – Best Attempt Autoinjector with Standard Label + Pictogram	Add footnote: "Note: If a subject has more than one attempt to self-administer study treatment at a single visit, the best attempt is included in this summary."	SAC
7.4	All Subjects	TAB_INJ1	Summary of the Proportion of Subjects Successfully Able to Self-Administer Injection by Visit – Best Attempt Autoinjector with Standard Label	Add footnote: "Note: If a subject has more than one attempt to self-administer study treatment at a single visit, the best attempt is included in this summary."	SAC
7.5	All Subjects	TAB_INJ2	Summary of Investigator Evaluation of User/Device Errors by Visit Autoinjector with Standard Label + Pictogram	Add footnote: "Note: If a subject has more than one attempt to self-administer study treatment at a single visit, only the first attempt is included in this summary."	SAC

No.	Population	IDSL / TST ID / Example Shell	Title	Programming Notes	Deliverable [Priority]
Evaluation of Autoinjector - Tables					
7.6	All Subjects	TAB_INJ2	Summary of Investigator Evaluation of User/Device Errors by Visit Autoinjector with Standard Label	Add footnote: "Note: If a subject has more than one attempt to self-administer study treatment at a single visit, only the first attempt is included in this summary."	SAC

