[1] Blood eosinophil count immediately before starting mepolizumab that was  $\geq 150$  cells/uL or a blood eosinophil count that was  $\geq 300$  cells/uL in the 12 months prior to starting mepolizumab.

[2] Subjects currently receiving treatment with mepolizumab only.

userid: /arenv/arprod/compound/study/final/drivers/drivername.sas DDMMYYYY HH:MM

Example TAB\_POP5  
Protocol: 204959  
Population: All Subjects (Safety)

Table X  
Summary of Previous Mepolizumab Clinical Trials

		Liquid Autoinjector (N=XX)
Did the subject participate in a previous mepolizumab trial?	n	XX
	No	XX (XX%)
	Yes	XX (XX%)
Protocol number	115666	XX (XX%)
	204471	XX (XX%)
	205667	XX (XX%)

Example TAB\_INJ1  
 Protocol: 204959  
 Population: All Subjects (Safety)

Table X  
 Summary of Proportion of Subjects Successfully Able to Self-Administer Injection by Visit - First Attempt  
 Autoinjector with Standard Label + Pictogram

Visit	Liquid Autoinjector (N = XX)		
	Attempted Injections	Successful Injections [1]	
	n (%)	n (%)	95% CI
WEEK 0	XX (XX%)	XX (XX%)	(XX%, XX%)
WEEK 4	XX (XX%)	XX (XX%)	(XX%, XX%)
WEEK 8	XX (XX%)	XX (XX%)	(XX%, XX%)
WEEK 4 and 8	XX (XX%)	XX (XX%)	(XX%, XX%)
WEEK 0, 4 and 8	XX (XX%)	XX (XX%)	(XX%, XX%)

[1] The denominator for the percentage of successful injections is the number of attempted injections.  
 Note: If a subject has more than one attempt to self-administer study treatment at a single visit, only the first attempt is included in this summary.

userid: /arenv/arprod/compound/study/final/drivers/drivername.sas DDMMYYYY HH:MM

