**CONFIDENTIAL**

204959

Example TAB\_INJ2  
 Protocol: 204959  
 Population: All Subjects (Safety)

Page 1 of 1

Table X.X  
 Summary of Investigator Evaluation of User/Device Errors by Visit  
 Autoinjector with Standard Label + Pictogram

Visit	n		Liquid Autoinjector (N=XX)
WEEK 0	XX	Was the drug successfully injected?	
		Yes	XX (XX%)
		No	XX (XX%)
		Not attempted	XX (XX%)
		User Error	
		Any User Error	XX (XX%)
		Ring cap not removed from autoinjector	XX (XX%)
		Autoinjector not properly activated on injection site (e.g., gold needle guard not flush with skin)	XX (XX%)
		Autoinjector used upside down	XX (XX%)
		Autoinjector pulled away before end of injection (i.e., before purple indicator stopped moving)	XX (XX%)
		Other	XX (XX%)
		Device Error	
		Any Device Error	XX (XX%)
		Autoinjector leaking	XX (XX%)
		Components missing / broken / cracked	XX (XX%)
		Inspection window not clear	XX (XX%)
		Cannot remove ring cap	XX (XX%)
		Bent needle	XX (XX%)
		Cannot push the gold needle guard down to activate (i.e., force too high)	XX (XX%)
		Autoinjector does not activate (after pressing gold needle guard down)	XX (XX%)

Note: If a subject has more than one attempt to self-administer study treatment at a single visit, only the first attempt is included in this summary.

userid: /arenv/arprod/compound/study/final/drivers/drivername.sas DDMMYYYY HH:MM  
 Programming Note: Continue for Week 4 and 8

Example TAB\_INJ3  
Protocol: 204959  
Population: All Subjects (Safety)

Table X.X  
Summary of Observer Checklist for In-Clinic Injections  
Autoinjector with Standard Label + Pictogram

Visit: WEEK 0

Liquid Autoinjector  
(N=XX)

---

Time from removal of pen from storage to injection (mins)	n	XX
	Mean	XX.X
	SD	XX.XX
	Median	XX.X
	Minimum	XX
	Maximum	XX
Confirm who will be administering the injection	n	XX
	Patient	XX (XX%)
	Caregiver	XX (XX%)
Subject/caregiver completed all the training required	n	XX
	Yes	XX (XX%)
	No	XX (XX%)
Subject/caregiver had instructions for use (IFU) available for review during injection (as recommended)	n	XX
	Yes	XX (XX%)
	No	XX (XX%)

[1] Subject / caregiver completed task easily without repeated reference to the IFU.

[2] Subject / caregiver completed task but with some difficulty or repeated reference to the IFU for assistance.

[3] Subject / caregiver was not able to (or did not) complete task after multiple attempts and reference to the IFU, or intervention was required.

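### Does the primary Week 8 success rate need a second version that counts every subject without a Week 8 attempt as a failure?

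*SAP*

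**What the plan says.** Protocol 9.4.1 and SAP 7.1 give the same rule for the primary endpoint: "The denominator for the percentage calculation will be the number of subjects attempting an injection at Week 8". The footnote to shell TAB_INJ1 in SAP 14.9 carries it into every row of the success tables: "The denominator for the percentage of successful injections is the number of attempted injections". That shell serves first-attempt Tables 7.1 and 7.2 and best-attempt Tables 7.3 and 7.4, all titled "Summary of the Proportion of Subjects Successfully Able to Self-Administer Injection by Visit".

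The general rule is available data without imputation, with one exception. SAP 7.1 provides: "If there are withdrawals from study treatment due to issues pertaining to the use of the autoinjector, a sensitivity analysis of the primary endpoint" is run. SAP 5.3 says how: "Missing injection success assessments for subjects withdrawing from study treatment due to issues with the autoinjector will be included in the analysis as injection failures". Records marked as not attempted for the same subjects are treated the same way. SAP 14.5.2 repeats the rule with a slightly different trigger, "if there are withdrawals from the study due to issues pertaining to the use of the autoinjector". The two triggers should pick out the same people, because Protocol 5.5 withdraws from the study anyone who permanently stops study treatment.

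On losses generally, SAP 14.5.1 adds: "Withdrawn subjects will not be replaced in the study".

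**The concern.** The endpoint is worded as a proportion of subjects, and SAP section 7 names All Subjects (Safety) as the population, meaning everyone with at least one attempt. The percentage nevertheless describes a later subset: those still in the study and attempting at Week 8. A subject who withdraws consent, is lost to follow-up, or meets a laboratory, ECG, liver or pregnancy criterion (Protocol 5.5.1) before the third dose is not in the denominator. The sensitivity analysis does not bring that subject back, because it is conditional on withdrawals attributed to the autoinjector and counts only those subjects. If no withdrawal is attributed to the device, no missing-data check of the primary endpoint is run.

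Suppose some subjects found the device hard to use but were recorded as leaving for another reason. The Week 8 rate and its interval, which are the headline result for each label, would then be somewhat too favourable, and no planned interval would show by how much.

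**Working it through.** **1. Inputs**
- 158 enrolled, up to 5% dropout over the whole study, about 150 with complete data, about 100 and 50 by label (Protocol 9.2.1).
- Exact (Clopper-Pearson) 95% CI (SAP 7.1). For x successes in n: lower limit = Beta quantile 0.025 with parameters (x, n − x + 1); upper limit = Beta quantile 0.975 with parameters (x + 1, n − x).
- Enrolled numbers per label are not given. Assumption: 158 split 2:1, so 158 × 2/3 = 105.3 and 158 × 1/3 = 52.7, rounded to 105 and 53. Success counts are also assumed, near the 96% row of the protocol's precision table.

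**2. The plan's own figures reproduce**
- 158 × 0.95 = 150.1, matching 150.
- 96/100 gives 90.07 to 98.90 and 48/50 gives 86.29 to 99.51. Protocol 9.2.2 shows 90, 99 and 86, 100.
- That table is built on completed subjects, so the planned precision already refers to a reduced denominator.

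**3. Every non-attempter counted as a failure**

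| Label, share missing at Week 8 | Attempters | All subjects | Fall in rate | Fall in lower limit |
|---|---|---|---|---|
| Pictogram, 2 of 105 (about 2%) | 99/103 = 96.12% (90.35, 98.93) | 99/105 = 94.29% (87.98, 97.87) | 1.83 | 2.37 |
| Standard, 1 of 53 (about 2%) | 50/52 = 96.15% (86.79, 99.53) | 50/53 = 94.34% (84.34, 98.82) | 1.81 | 2.45 |
| Pictogram, 5 of 105 (about 5%) | 96/100 = 96.00% (90.07, 98.90) | 96/105 = 91.43% (84.35, 96.01) | 4.57 | 5.72 |
| Standard, 3 of 53 (about 5%) | 48/50 = 96.00% (86.29, 99.51) | 48/53 = 90.57% (79.34, 96.87) | 5.43 | 6.95 |

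The 5% rows are a ceiling under the protocol's assumption. They need all the dropout, which is assumed over the study to Week 12, to fall before the Week 8 dose, and every such subject to have failed.

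**4. Opposite extreme.** If all the missing subjects had succeeded, (96 + 5)/105 = 96.19% and (48 + 3)/53 = 96.23%, rises of 0.19 and 0.23 points.

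**5. Comparison with planned precision.** The planned interval widths at 96% are 98.90 − 90.07 = 8.83 and 99.51 − 86.29 = 13.22 points. Falls of about 2.4 points in the lower limit at 2% missing are small beside these. The ceiling falls are not negligible, but they are bounds.

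**6. What a reader of the planned output will have**
- TAB_INJ1 prints group N, attempted n (%) and successful n (%). Dividing successes by N gives the all-subjects rate, and its exact interval follows from the same two counts.
- Shell TAB_INJ2 reports Yes, No and "Not attempted" by label and visit, continued to Week 8. It does not state the denominator of its percentages. Whether that is n or N, subjects recorded as not attempting appear to be inside it, so a success percentage not restricted to attempters appears to be planned, without a CI.
- Tables 6.4 and 6.5 summarise discontinuation and disposition. Listings 3, 4 and 16 give each subject's reason for stopping treatment, reason for withdrawal and injection assessments.

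**The case for a change.** The best argument for adding the row is that the existing sensitivity analysis depends on how a withdrawal reason was recorded. The SAP gives no rule for deciding which withdrawals are due to the autoinjector. A subject who struggled with it and was coded as withdrawing consent would be missed, and a bound over all subjects would not depend on that coding. The cost is one row per table and no new data.

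The factual part stands: attribution is a judgement, and no interval over all subjects is listed. The remedy, though, answers a different question. The endpoint is success at an observed third dose, and someone withdrawn earlier for pregnancy or liver chemistry has no third dose to observe. Counting that person as a failure measures retention together with usability, so the row would have to be labelled as not estimating usability. It would not show which withdrawals were miscoded; the listings of reasons are the place to look for that. The row would also put two Week 8 percentages with different denominators in the primary table.

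A further route, staying in the study with no Week 8 attempt, is possible but narrow. Protocol 5.6 defines completion by the Week 12 visit, but Protocol 4.2 describes a completer as someone who also keeps to the treatment schedule, and permanent discontinuation means leaving the study. A single skipped dose remains possible and has its own category in TAB_INJ2.

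**Conclusion.** No change is needed. Using attempters as the denominator is a fair choice for a device-use endpoint. It is pre-specified, agrees between protocol and SAP, and is supplemented where missingness is attributed to the autoinjector. Protocol 9.1 rules out hypothesis testing and any comparison between labels, and no success threshold is set, so no decision turns on the second figure.

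The most the rate could move is about 4.6 points (pictogram) or 5.4 points (standard label). That assumes a 105/53 split, 96% success among attempters, the full 5% dropout before Week 8 and every such subject failing. At about 2% missing the movement is about 1.8 points. Both figures can be derived from counts the planned tables already print. An analyst who wants to quote the all-subjects bound with an exact interval in the study report can do so without amending the plan; that is a reporting preference and corrects no error.
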